136 have been performed within the last 6 months and of high quality (at the discretion of the
137 investigator) it is not required to repeat this. Questionnaires regarding symptoms and
138 quality of life (see 8.4) are filled in by the patients.

139

140 **General follow up**

141 Patients that are randomised to endoscopic balloon dilation will be asked to fill in an
142 Eckardt score three weeks after the dilation. If this score is still more than 3, they will be
143 scheduled to undergo a second pneumatic dilation, but now using a 35 mm balloon
144 (figure 1). Manometry is performed if the Eckardt score is 3 or less. If the manometry

145 shows an IRP of more than 10, patients will also undergo a second pneumatic dilation
 146 (with a 35 mm balloon).
 147 Manometry and timed barium oesophagography are performed and questionnaires are
 148 filled in all patients 3 months after treatment and at 1, 2 and 5 years after treatment.
 149 Twenty-four hour pH-impedance monitoring is performed one year after treatment to
 150 evaluate oesophageal acid exposure. Upper endoscopy is performed at 1, 2 and 5 years
 151 after treatment.
 152
 153
 154

155
 156 *Figure 1 Treatment algorithm used in this study*
 157

158
 159
 160
 161
 162
 163

	Baseline	3 weeks*	3 months	1 year	2 years	5 years
Blood count, chemistry, clotting	X					
Questionnaires	X	Eckardt*	X	X	X	X
Timed barium oesophagography	X		X	X	X	X
Manometry	X	If Eckardt >3*	X	X	X	X
Upper endoscopy	X			X	X	X
pH-impedance monitoring				X		

164

165

Table 1 Schedule of baseline and follow-up examinations; * only for patients randomised to balloon dilation

166

167

168 **8.2 Pneumodilation (PD)**

169 In this study pneumodilation will only be performed by experienced endoscopists, that
170 have performed over 20 pneumodilation procedures. Patients are asked to use clear
171 fluids only starting 24 hours before the procedure and nil per mouth starting 8 hours
172 before the procedure. Under fluoroscopic guidance a Rigiflex balloon (Boston Scientific)
173 is positioned at the esophagogastric junction and dilated at a pressure of 5 PSI, followed
174 by dilation with 8 PSI for one minute (Figure 2).^{8,10} The initial pneumatic dilation is
175 performed using a 30-mm balloon. Three weeks later the symptoms of patients are
176 evaluated using the Eckardt score. If the Eckardt score is still higher than 3, a
177 subsequent dilation with a 35-mm balloon is scheduled. If the Eckardt score is less than

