178 3 a subsequent high-resolution manometry is scheduled. If this shows an integrative
179 relaxation pressure (IRP4) of more than 10 mmHg, a subsequent dilation with a 35-mm
180 balloon is scheduled as well. In total, patients will thus undergo one or two pneumatic
181 dilations in the first 6 weeks. A second dilation within this 6 week period is not
182 considered a failure but considered part of the regular treatment. PPI are taken orally in
183 a single daily dose for two weeks after each dilation.

[figure not shown]

Figure 2 Schematic outline of a pneumatic balloon dilation

[figure not shown]
184
185
186
187

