250 The average follow-up after the procedure described in the different articles was 3-5
251 months. No serious complications were observed during this follow-up period.
252 Furthermore none of the patients developed recurrent symptoms and symptoms of
253 gastro-esophageal reflux or reflux esophagitis were minimal.

254

255 **8.3.2** *Risk of complications in POEM in the first treated patients of the AMC*

256 In the AMC the POEM procedure is performed in more than 10 patients. There
257 were no serious adverse events (SAEs) preoperative or postoperative.
258 Preoperative two adverse events occurred in different patients. In one patient a
259 minor bleeding occurred during the cutting of the circular muscle layer which was
260 easily controlled by endoscopic coagulation. To be certain that the patient didn't
261 develop a rebleed, the patient stayed longer at the recovery for close monitoring.
262 Another adverse event that occurred during the procedure was a
263 pneumoperitoneum due to small transmural dissections into the mediastinum.
264 The pneumoperitoneum caused a temporary elevation of intraperitoneal pressure
265 which was relieved with an 18G canula, placed in the abdominal wall during the
266 procedure. The adverse events didn't extend the hospital admission and
267 reintervention was not needed.

268 Postoperative complications didn't occur. At this moment the follow-up period of
269 the treated patients is 1-6 months. None of the treated patients developed
270 recurrent symptoms so far and also gastro-esophageal reflux symptoms aren't
271 registered.

272

273 **8.4** *Questionnaires*

- 274 • Eckardt score, which is the sum of symptom scores for dysphagia, regurgitation,
275 chest pain and weight loss. Each symptom is scored from 0 to 3. The minimum
276 score is 0, the maximum 12. (see appendix A for explanation of the calculation of
277 the score)
- 278 • Medical Outcomes Study 36-Item Short-Form Health Survey [SF-36], The SF-36
279 mental and physical summary scores (which range from 0 to 100, with higher
280 scores indicating better well-being) measure general aspects of health quality of
281 life (12).

- 282 • The validated Achalasia Disease-Specific Quality-of-Life questionnaire
283 (achalasia-DSQoL).¹³
- 284 • The Gastroesophageal Reflux Disease Questionnaire (GerdQ) is a self-
285 assessment questionnaire that can be used for the diagnosis and follow-up of
286 gastroesophageal reflux disease, and measures both symptoms and impact of

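### The three-week manometry rule in the pneumodilation arm is stated three different ways, and section 8.2 gives no action for an Eckardt score of exactly 3

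*Protocol*

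**What the plan says.** Three places govern the three-week assessment after the first (30-mm) dilation.

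- **Section 8.1, General follow up.** Patients complete an "Eckardt score three weeks after the dilation. If this score is still more than 3, they will be" booked for a second dilation with the 35-mm balloon. For the rest, "Manometry is performed if the Eckardt score is 3 or less", and an IRP above 10 also leads to the 35-mm dilation.
- **Section 8.2, Pneumodilation (PD).** Symptoms are "evaluated using the Eckardt score. If the Eckardt score is still higher than 3, a" 35-mm dilation follows. The next sentence begins "If the Eckardt score is less than" and goes on "3 a subsequent high-resolution manometry is scheduled". An IRP4 above 10 mmHg then leads to the 35-mm dilation.
- **Table 1.** The manometry row, in the three-week column, is conditional on an Eckardt score above 3. An asterisk marks this as "only for patients randomised to balloon dilation".

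Section 8.2 adds that a second dilation within the six-week period is not "considered a failure but considered part of the regular treatment". Section 8.4 defines the Eckardt score as a sum of four symptoms: "Each symptom is scored from 0 to 3", so the total runs from 0 to 12.

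**The concern.** This rule decides treatment as well as measurement. For a PD patient whose score has fallen to 3 or less, the three-week manometry is the only stated route to the 35-mm dilation. Manometry is repeated at 3 months, but no dilation trigger is attached to it.

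The rule also touches the primary endpoint. Under section 5, an optional second dilation belongs to the initial treatment, while later retreatment counts against success. Take a patient who scores 3 and has a high IRP4. Under section 8.1 that patient gets a second dilation that is not a failure. Under a literal reading of section 8.2 or Table 1 the patient does not, and a dilation needed later would count as a failure. Any such effect would plausibly count against PD, the comparator, in a trial that expects POEM to be better. The protocol does not show that this happened.

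The trial is multi-centre. Section 8.2 describes the PD procedure and Table 1 is the visit schedule, and centres could reasonably work from either.

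**Working it through.** **The protocol's own figure.** The point does not depend on the sample size, but the sample size gives the scale. Section 11 assumes 70% (PD) and 90% (POEM) success, two-sided alpha 0.05 and power 80%. With the pooled-variance formula for two proportions and no continuity correction:

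n = [1.960 × √(2 × 0.80 × 0.20) + 0.842 × √(0.70 × 0.30 + 0.90 × 0.10)]² / 0.20² = (1.109 + 0.461)² / 0.04 = 61.6, rounded up to 62 per group.

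This matches the stated 62; power at 62 per group is 80.3%.

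**The three rules applied to every score.** Four items scored 0 to 3 give totals from 0 to 12, which is 13 attainable scores.

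| Eckardt score at 3 weeks | Section 8.1 | Section 8.2 | Table 1 (manometry only) |
|---|---|---|---|
| 0–2 (3 scores) | manometry | manometry | no manometry |
| 3 (1 score) | manometry | no action stated | no manometry |
| 4–12 (9 scores) | 35-mm dilation | 35-mm dilation | manometry |

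- Section 8.1 assigns an action to 4 + 9 = 13 of 13 scores.
- Section 8.2 assigns an action to 3 + 9 = 12 of 13. The gap is at 3.
- Table 1 agrees with section 8.1 on who has manometry at 0 of 13 scores.

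**Which rule is intended.** The cut-off elsewhere is the one in section 8.1: success is 3 or less (section 5), and inclusion (section 7.2) and failure (addendum) are above 3. Section 8.1 is also the only version that covers every score and agrees with the direct route to dilation above 3.

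**Possible size.** The protocol does not say how many PD patients would score exactly 3, so any share is an assumption. Planned PD patients: 130 / 2 = 65.

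| Assumed share scoring exactly 3 | Patients |
|---|---|
| 5% | 65 × 0.05 = 3.25 |
| 10% | 65 × 0.10 = 6.5 |
| 20% | 65 × 0.20 = 13 |

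Only those with IRP4 above 10 mmHg could miss a dilation, and only if their centre followed section 8.2 or Table 1. One changed two-year outcome moves the PD success rate by 1 / 65 = 1.54 percentage points, against the assumed difference of 90% − 70% = 20 points.

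**The case against.** The best case for leaving this alone is that sections 8.1 and 8.2 do not strictly contradict each other. Section 8.2 is silent at 3 and does not forbid manometry there. Section 8.1 covers every score, and a centre reading the whole protocol would apply it. The Table 1 cell rests on one symbol in a table read from a PDF. If printed that way, it is an obvious slip, because both text sections send scores above 3 straight to dilation. Figure 1, the treatment algorithm cited at this step, is not reproduced in the text available for review and may show what centres actually followed. Section 5 allows the optional second dilation within three months, which leaves some room for a later one. Few patients can be affected, and counts of scores are not counts of patients.

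Much of this stands. Section 8.1 is very probably the intended rule, the Table 1 entry should be checked against the printed page, and the effect is probably small. But the gap in section 8.2 is in plain words and does not depend on the table. Figure 1 could show the intention, but it could not make the two sections and the table agree. The three-month allowance in section 5 attaches no pressure check or trigger, so it does not replace the missed one. The addendum deals with retreatment after failure and does not restate the three-week rule.

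**Conclusion.** The concern holds. The protocol gives three different conditions for the three-week manometry. Section 8.2 leaves an attainable score, exactly 3, without an action, and Table 1 as extracted reverses the rule. Followed as written, either would withhold a check that section 8.1 requires and that decides part of the initial PD treatment.

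The practical effect cannot be computed from the protocol and is probably small: roughly 3 patients for each 5% of the PD arm scoring exactly 3, fewer once restricted to those with IRP4 above 10 mmHg, and about 1.5 points on the PD success rate per changed outcome. This rests on 65 PD patients as planned and on an assumed share scoring 3. Following Table 1 alone would reach further, since it omits the check at every score of 3 or less, but that depends on the cell being printed as extracted. The design and sample size are not affected. The correction should be made, but the trial's validity does not turn on it.

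**What to change.** Adopt the section 8.1 rule everywhere:

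- In section 8.2, change the manometry condition to an Eckardt score of 3 or less.
- In Table 1, after checking the printed version, change the three-week manometry entry to Eckardt ≤ 3, PD arm only.
- Confirm that Figure 1 shows the same rule.
- Notify all centres, and look up how PD patients with a three-week score of exactly 3 were handled.

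The cost is one phrase, one table cell, a check of the figure, a notice and a short review of records. Nothing changes in the design or the sample size.

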8.3 Per-oral endoscopic myotomy (POEM)

189 In this study POEM will only be performed by experienced endoscopists, that have
190 performed over 10 POEM procedures. Patients are admitted two hours prior to the
191 POEM procedure and are discharged the next day. Patients are asked to use a diet with
192 clear fluids starting 24 hours before the procedure and nil per mouth starting 8 hours
193 before the procedure. On the day of the procedure, antibiotics and double dose PPI
194 (proton pump inhibitor) are administered intravenously. A PPI will be taken orally for two
195 weeks in a single daily dose starting at the day of treatment. POEM is performed under
196 general anesthesia and with endotracheal intubation. The mouth, throat and esophagus
197 are rinsed with saline and chlorhexidine (40–60 ml). POEM procedures are then
198 performed as described by Inoue et al. (figure 3).⁸

199 A forward-viewing upper endoscope (GIF H180J; Olympus, Hamburg, Germany) is used
200 with a transparent distal cap (MH 588; Olympus). Carbon dioxide gas is used for
201 insufflation during the procedures. An endoscopic dissection knife (KD-640L
202 TriangleTipKnife; Olympus) is used to access the submucosa, to create the submucosal
203 tunnel, and also to divide circular muscle fibers over a minimum length of 6 cm in the
204 esophagus, and 2 cm onto the cardia according to the standards of surgical myotomy.
205 An electrogenerator (Erbe Vio 300D; Erbe Elektromedizin, Tübingen, Germany) is used

206 with Endocut Q mode (effect 2) to open the mucosa, and spray coagulation mode (effect
 207 2, 50 watt) to dissect the submucosa and divide the muscle fibers. A coagulating forceps
 208 (FD-410LR Coagrasper; Olympus) is used for hemostasis as needed. Closure of the
 209 mucosal entry site is performed using standard endoscopic clips (HX-110UR EZ Clip
 210 Reusable Rotatable Clip Fixing Device and HX-610-135L Single Use Clips; Olympus).
 211 On the next day postoperative fluoroscopy is performed to rule out a leak at the
 212 esophageal closure site before discharge. Patients are kept nil per mouth until after the
 213 fluoroscopy and are kept on a liquid diet for an additional 24 h. Patients are discharged
 214 with single dose PPI and a soft diet for 2 weeks.
 215

216
 217
 218

Figure 3 Schematic outline of the POEM procedure ¹¹

219 **8.3.1** *Risk of complications in POEM from recent clinical studies*

220 So far there is limited information about the complications related to the POEM
221 procedure because it is a relative new procedure and long-term follow-up is not yet
222 available. Serious adverse events are not described in the previous studies that
223 performed POEM. The main preoperative complications that are described are
224 subcutaneous emphysema, pneumoperitoneum and pneumothorax. Transmural
225 openings into the mediastinum and into the peritoneal cavity caused emphysema,
226 pneumoperitoneum and pneumothorax. During POEM the inner circular muscle layer is
227 separated from the outer longitudinal muscle layer, leaving the longitudinal muscles
228 intact.⁹ The longitudinal muscle fibers are extremely thin, so minor damage can lead to
229 transmural dissections into the mediastinum and peritoneal cavity.

230 Subcutaneous emphysema was treated conservatively and in all cases the emphysema
231 resolved spontaneously in 2-3 days after surgery. The treatment of the
232 pneumoperitoneum occurred in all patients during the operation. A needle or canula of
233 18G was placed in the abdominal wall which gave directly relieve.^{8,9} A pneumothorax
234 was a rare complication and in all cases thoracic drainage was administered during the
235 operation which gave immediately relieve. Other described rare complications
236 preoperatively were a minor bleeding, controlled by endoscopic coagulation, and small
237 perforations which were clipped.

238 Postoperative complications were rare. One article described pneumothorax as an
239 important postoperatively complication.¹² The treatment was in most patients
240 conservatively and in some patients a thoracic drainage was administered, dependent
241 on the lung compression volume. An uncommon postoperative complication was a
242 delayed hemorrhage, one day after the operation. This occurred in one patient and was
243 probably caused by a bleeding in the submucosal tunnel. A three-cavity tube was placed
244 by endoscopy into the stomach and lower part of the esophagus to compress the
245 bleeding. After four days the tube was removed without further complications. Another
246 rare complication was a superficial ulcer (Forrest III) at the cardia that was detected with
247 a control endoscopy two days after POEM. This was only seen in one patient. The
248 patient had to continue PPIs and the hospital stay was extended. The control endoscopy
249 7 days after the procedure showed healing of the ulcer.

250 The average follow-up after the procedure described in the different articles was 3-5
251 months. No serious complications were observed during this follow-up period.
252 Furthermore none of the patients developed recurrent symptoms and symptoms of
253 gastro-esophageal reflux or reflux esophagitis were minimal.

254

255 **8.3.2** *Risk of complications in POEM in the first treated patients of the AMC*

256 In the AMC the POEM procedure is performed in more than 10 patients. There
257 were no serious adverse events (SAEs) preoperative or postoperative.
258 Preoperative two adverse events occurred in different patients. In one patient a
259 minor bleeding occurred during the cutting of the circular muscle layer which was
260 easily controlled by endoscopic coagulation. To be certain that the patient didn't
261 develop a rebleed, the patient stayed longer at the recovery for close monitoring.
262 Another adverse event that occurred during the procedure was a
263 pneumoperitoneum due to small transmural dissections into the mediastinum.
264 The pneumoperitoneum caused a temporary elevation of intraperitoneal pressure
265 which was relieved with an 18G canula, placed in the abdominal wall during the
266 procedure. The adverse events didn't extend the hospital admission and
267 reintervention was not needed.

268 Postoperative complications didn't occur. At this moment the follow-up period of
269 the treated patients is 1-6 months. None of the treated patients developed
270 recurrent symptoms so far and also gastro-esophageal reflux symptoms aren't
271 registered.

272

273 **8.4** *Questionnaires*

- 274 • Eckardt score, which is the sum of symptom scores for dysphagia, regurgitation,
275 chest pain and weight loss. Each symptom is scored from 0 to 3. The minimum
276 score is 0, the maximum 12. (see appendix A for explanation of the calculation of
277 the score)
- 278 • Medical Outcomes Study 36-Item Short-Form Health Survey [SF-36], The SF-36
279 mental and physical summary scores (which range from 0 to 100, with higher
280 scores indicating better well-being) measure general aspects of health quality of
281 life (12).

- 282 • The validated Achalasia Disease-Specific Quality-of-Life questionnaire
283 (achalasia-DSQoL).¹³
- 284 • The Gastroesophageal Reflux Disease Questionnaire (GerdQ) is a self-
285 assessment questionnaire that can be used for the diagnosis and follow-up of
286 gastroesophageal reflux disease, and measures both symptoms and impact of
287 symptoms on person's daily life

288

289 **8.5** *Timed barium oesophagography*

290 In the timed barium oesophagography technique, upright frontal spot films of the
291 esophagus are obtained at 1, 2, and 5 min after ingestion of 100-200 ml of low-density
292 (45% weight in volume) barium sulphate (volume of barium determined by patient
293 tolerance).¹⁴ This is a routine clinical test that is used to measure oesophageal emptying
294 and reflects oesophageal function.

295

296 **8.6** *High resolution manometry of the oesophagus*

297 High resolution manometry of the oesophagus (pressure measurement) is the gold
298 standard to diagnose achalasia and is used in clinical practice to evaluate the effect of
299 the treatment. High resolution manometry is performed using a catheter that is
300 introduced into the oesophagus transnasally. Patients will swallow 10 small sips of 5 mL
301 of water and presence of peristalsis, spasms and lower oesophageal sphincter pressure
302 and relaxation during swallowing are evaluated. Classification of achalasia will be done
303 using the revised Chicago classification.¹⁵ In routine clinical practise oesophageal
304 manometry is often performed in patients with achalasia.

305

306 **8.7** *Impedance-pH recording*

307 It is known that patients that underwent pneumodilation or myotomy are prone to
308 develop gastro-oesophageal reflux disease and often have a high oesophageal acid
309 exposure time.¹⁶ Twenty-four hour impedance-pH recording is performed to assess the
310 degree of oesophageal acid exposure. During the test, a small catheter is introduced
311 transnasally into the oesophagus.¹⁷ This catheter consists of impedance and pH sensors
312 that measure reflux episodes and 24 hour data is stored on a datalogger which patients
313 carry on their belt. Measurements are performed after cessation of acid-suppressive

314 medication for at least 7 days. Measurements are analyzed for acid exposure time (time
315 with pH<4), number of acid and number of weakly acid reflux episodes and duration of
316 reflux episodes. In the analysis of the pH signals, episodes with pH < 4 caused by stasis-
317 associated acidification of oesophageal contents will be discarded. Impedance-pH
318 monitoring is a routine clinical test for assessment of oesophageal acid exposure.

319

320 **8.8** *Upper endoscopy*

321 The main reason to perform upper endoscopy at baseline is to exclude pseudoachalasia
322 and other causes of dysphagia. After treatment, the main reason to perform upper
323 endoscopy is to investigate whether oesophagitis is present. The degree of oesophagitis
324 is scored according to the LA classification.¹⁸ Upper endoscopy is performed after
325 cessation of acid-suppressive medication for at least 10 days. Upper endoscopy is
326 performed according to the local routine protocol, sedation with midazolam and/or
327 fentanyl is possible if patient prefers this. It is routine clinical practise to perform regular
328 upper endoscopies in patients with achalasia.

329

330 **8.9** *Withdrawal of individual subjects*

331 Participants can leave the study at any time for any reason if they wish to do so without
332 any consequences. The investigator can decide to withdraw a subject from the study for
333 urgent medical reasons.

334

335 **8.9** *Premature termination of the study*

336 Efficacy data of the study will be monitored by the investigators, mainly by the PI, in
337 cooperation with the DSMB. The study can be early terminated because of clear benefit,
338 harm or futility. Because the first results of the POEM in the AMC and other foreign
339 centres are promising, symptom improvement and lower oesophageal sphincter
340 pressure reduction are comparable to the current two treatments, it is not likely this study
341 will be terminated prematurely. However the aim of this study is to look at the efficacy of
342 POEM versus PD and therefore we need to define stopping regulations for the study of
343 the primary endpoint, treatment success.

344 The stopping regulation will only be based on the occurrence of severe complications,
345 SAEs, associated with the treatment and re-intervention postoperative. After each

346 inclusion of 20 participants the study team and the DSMB will discuss the data and
347 review the stopping regulations. The incidence of SAEs in pneumodilation is normally
348 around the 5%. Because POEM is a new procedure at the moment the incidence of
349 SAEs is unknown. One of the stopping regulations concern SAEs and states that the
350 incidence of SAE's in both groups shouldn't exceed 10%. The other stopping regulation
351 is if the incidence of re-intervention exceeds 20%, 1 year postoperative. This is
352 applicable for both treatments. For pneumodilation the incidence for re-intervention is
353 estimated on 10%, 1 year postoperative.

354

355 **9 SAFETY**

356 **9.1** *Section 10 WMO event*

357 In accordance to section 10, subsection 1, of the WMO, the investigator will inform the
358 subjects and the reviewing accredited METC if anything occurs, on the basis of which it
359 appears that the disadvantages of participation may be significantly greater than was
360 foreseen in the research proposal. The study will be suspended pending further review
361 by the accredited METC, except insofar as suspension would jeopardise the subjects'
362 health. The investigator will take care that all subjects are kept informed.

363

364 **9.2** *Adverse and serious adverse events*

365 Pneumodilation is a safe and regularly performed procedure for patients with achalasia.
366 In this study the procedure will be performed by experienced endoscopists, that have
367 performed over 20 pneumodilations. Complications due to a pneumodilation are rare and
368 the main complication is an oesophageal perforation. The treatment of a perforation is
369 frequently conservatively, total restriction of food and drinks and intravenous antibiotic
370 therapy. In some cases surgery is needed. The incidence of a perforation during
371 pneumodilation is approximately 3%.⁶

372 POEM is a relative new procedure in the treatment of achalasia. In Germany and Japan
373 the first POEM procedures were performed and in the AMC so far 10 patients are
374 treated with POEM. Because the follow-up of the first patients is only 3-5 months,
375 nothing is known about long-term complications or efficacy. Major complications that can
376 occur during the procedure are a bleeding or oesophageal perforation. Treatment can
377 directly be performed during the procedure by clipping the bleeding or perforation. In

378 some cases a surgical procedure can be needed. Furthermore POEM can be
379 complicated by minor complications, like pneumoperitoneum and postoperative
380 subcutaneous emphysema. Pneumoperitoneum can be relieved by a puncture of the
381 abdominal wall using an 18-gauge needle during the procedure. Postoperative
382 subcutaneous emphysema is usually self-limiting and additional treatment is not needed.
383 So far the only complications that occurred in the treated patients of the AMC were a
384 minor bleeding that was stopped during the procedure and one patient developed a
385 pneumoperitoneum which relieved by a puncture of the abdominal wall using an 18-
386 gauge needle during the procedure.

387 All the additional measurements that are performed before and after treatment are safe
388 procedures and routinely performed in the clinical setting. Possible complications are
389 mainly due to placement of the catheters and endoscope. The catheters can give
390 discomfort in the nose and pharynx. Furthermore in rare cases a mucosal bleeding of
391 the nose, caused by the catheter, can occur which never need extra treatment. The
392 endoscope can give discomfort in the pharynx.

393

394 All adverse events reported spontaneously by the subject or observed by the
395 investigators will be recorded in a database. The Data Safety Monitoring Board will be
396 informed about the adverse events.

397

398 All serious adverse events (SAEs) will be reported through the web portal
399 *ToetsingOnline* to the accredited METC that approved the protocol. The SAEs will be
400 reported within 15 days after the sponsor is first notified of the SAEs.

401 The SAEs that result in death or are life treating will be reported expedited through the
402 web portal *ToetsingOnline* to the accredited METC that approved the protocol. This will
403 not occur later than 7 days after the coordinating investigators and principal investigator
404 have knowledge of the SAE(s). This first report is preliminary and within 8 days after
405 submission of the first report a final report will be submitted.

406

407 **9.3** *Follow-up of adverse events*

408 All adverse events will be followed until they have abated or until a stable situation has
409 been reached. Depending on the event, follow up may require additional tests or medical

410 procedures as indicated, and/or referral to another medical specialist. Furthermore a
411 Data Safety Monitoring Board will be informed about the adverse events that occur.

412

413 **9.4** *Data Safety Monitoring Board (see also the DSMB charter)*

414 A Data Safety Monitoring Board (DSMB) is established. In total the DSMB will consist of
415 four members, an epidemiologist, a surgeon, a paediatrician specialised in
416 gastroenterology and a gastroenterologist. None of the members have a conflict of
417 interest with the sponsor of the study. Personal details of the DSMB members can be
418 found in the DSMB charter which also describes in detail the function, aims and
419 responsibilities of the DSMB. In short the DSMB will act in an independent, expert and
420 advisory capacity to monitor participant safety and evaluate the efficacy and the overall
421 conduct of the study. The DSMB will be informed about adverse events and serious
422 adverse events that occur during the study. The advice(s) of the DSMB, in case it
423 influences the set-up of the study, will be notified upon receipt by the sponsor to the
424 METC that approved the protocol. With this notification a statement will be included
425 indicating whether the advice will be followed.

426

427 **10 STATISTICAL ANALYSIS AND RANDOMISATION**

428 We aim to perform an intention to treat analysis. After testing for normality, pairwise
429 comparisons will be performed between the two treatment arms for all primary and
430 secondary outcomes. Categorical variables will be compared using the Chi-square test.
431 The success rates of the two treatment arms will be compared using log-rank tests on
432 Kaplan-Meier estimates.

433 Randomisation will be done using a web-based online available program and is stratified
434 for each participating centre.

435

436 **11 SAMPLE SIZE ANALYSIS**

437 Recently reported complication free success rate of a two step PD strategy is 68% at
438 two years.⁶ Long term outcome data of POEM is lacking but at three months a success
439 rate of 94% has been described.⁹ Assuming success rates of 70% for PD and 90% for
440 POEM after two years, we estimated that with 62 patients in each group, the study would
441 have 80% power to detect a significant difference in success rate between PD and

442 POEM with a two-sided alpha level of 0.05. To cope with an estimated 5% loss to follow-
443 up, we aim to enrol 130 patients.

444

445 **12 PRIVACY**

446 The data of the subjects are coded in order of participation. The code and the data are
447 stored in different locations. The code can only be seen by the investigators. Qualified
448 authorities can get insight in code and data, but only when accompanied by the
449 investigators. Data will be stored 20 years after closure of the trial.

450

451 **13 ETHICAL CONSIDERATION**

452 The protocol of this study will be submitted to the Medical Ethical Committee of the
453 Academic Medical Center and will not start before formal approval has been granted.
454 Participants will be given oral and written explanation about the study, before they give
455 written informed consent. Subjects are allowed to withdraw informed consent without
456 providing arguments.

